from this study, and design of a large-scale follow up trial to test the effectiveness of the improved intervention.

6. Participant Enrollment and Withdrawal

Participant Inclusion Criteria

Participants will be eligible to participate in the study if they:

- Are 18 years or older
- Have an iPhone or Android phone
- Are a U.S. resident
- Are not in another form of alcohol treatment
- Are actively drinking in the past 3 months
- Have English language proficiency
- Are not using another mHealth alcohol intervention
- Score on the USAUDIT between an 8 to 24 for males under 65
- Score on the USAUDIT between a 7 to 24 for females and males over 65 on the USAUDIT
- Electronically sign the consent form

For the interviews, from back-end data capture we will determine high and low users by the amount of time they spend using the app or the chatbot. High utilizers will be selected from amongst those participants in the top third of each intervention's use (based on total frequency and duration of use) and low utilizers will be selected from those in the bottom third for each intervention. Only participants in either the app or the chatbot intervention groups will be randomly selected to be interviewed.

Participant Exclusion Criteria

Participants will be excluded from participating if they indicate they are:

- more than 30 days abstinent at baseline
- in alcohol or drug abuse treatment currently
- pregnant or nursing
- having a moderate to severe level of alcohol use disorder, defined as having a score of 25 or higher on the USAUDIT
- unwilling or unable to complete follow-up assessment
- not residents of the U.S.
- unable to read or text in English

Recruitment and Enrollment

Participant recruitment will be conducted through Facebook advertisements. The advertisements will provide a link to the study website which will describe the study and provide a link to the prescreen survey. Facebook analytics will be reviewed weekly by the graduate research assistant and project manager. Analytics will be reviewed on each of the ads for which ads are more successful at recruiting interested participants and the demographics the ads are more successful at recruiting. These analytics will inform how to alter advertisements if the sample being recruited is largely one race or gender. Recruitment will begin in June 2020 and will end when the target sample is reached.

Prescreen

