A prescreen survey will be hosted through Qualtrics. It will survey for eligibility criteria which includes demographic questions and the US AUDIT screening questionnaire. Participants will be automatically directed to the consent form hosted on Qualtrics if they are eligible. They will automatically be directed to a debriefing screen and resources if they are not eligible. The AUDIT is the most widely used alcohol screening test in the world with more than 25 years of validation studies worldwide. We will use the USAUDIT, a recent adaptation of the original AUDIT that uses U.S. standard drink amounts and NIAAA drink limits. A score of 8 or greater on the USAUDIT suggests that they are at risk of experiencing significant problems from drinking alcohol. This cut point has been found to yield high sensitivity and specificity when compared to a number of criteria for problematic alcohol use (e.g., alcohol dependence); thus, numerous studies have found it to be an accurate screening tool for alcohol problems among numerous groups including women and older adults. In the current study, the standard cut point of 8 for men and 6 for women and men over 65 will be used to establish problem drinking. Participants with high likelihood of alcohol dependence, evidenced by a score of 25 or above will be screened out of the study.

Target Sample Size

The target sample size is a minimum of 50 participants per intervention arm (i.e., app group, chatbot group, delay group). This will provide adequate power to detect modest effect sizes, pre to post, in outcomes for pilot purposes. For the interviews, 20 participants (10 from the app group and 10 from the chatbot group) will be randomly selected and asked to participate.

Participant Withdrawal or Termination

Participants are free to withdraw from participation in the study at any time upon request. An investigator may terminate participation in the study if the participant meets an exclusion criterion (either newly developed or not previously recognized) that precludes further study participation.

7. Study Procedures and Schedule

This study will consist of three phases. Phase I will focus on developing the AI chatbot version of Step Away and developing procedures for the pilot study, including evaluating the different program elements using an expert panel.

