- The treatment history section of the Form 90 will be modified to be administered online at baseline and follow-up, to gather lifetime treatment history, self-help attendance, and treatment use.
- Readiness to Change. We will utilize the Readiness to Change Treatment Version (RCQTV), which RCQTV has been shown to have solid reliability and validity and has been modified for individuals contemplating or engaged in treatment for alcohol problems.

Follow-Up

The US AUDIT, TLFB, SIP-R, and Readiness to Change questionnaires will be used for the follow-up assessments. In addition, those in the app and chatbot groups will be asked to complete the System Usability Scale to assess their perceptions of the interventions' usability. The follow-up survey will be sent to participants at 4 months post-enrollment.

Interviews

Interviews will be conducted after the completion of the follow-up survey. Interview questionnaires will focus on users' experiences with the app or the chatbot. These interviews will be conducted over the phone.

8. Assessment of Safety

Several safety measures will be put in place to ensure the safety, comfort, and confidentiality of all participants. Care will be taken to inform potential participants fully before they consent to participate about all potential risks that may arise from their participation. The two most important aspects of participant protection in the proposed work are assuring the adequacy of informed consent (including full disclosure of all potential risks) and protecting confidentiality. To minimize risk, we will clearly explain all procedures to participants in our informed consent documents and clearly outline safeguards for confidentiality implemented in the study. Further, in order to protect their confidentiality, all participants will be encouraged to set a password to access their smartphone home screen.

Also, a Data Safety Monitoring Board (DSMB) will be convened in Year 1 of the project and will include the following two members with expertise in psychology, behavioral health, and

research ethics. The DSMB will meet twice during each year of the project to review the status of the project.

9. Statistical Considerations

All randomized study participants who complete both the baseline and follow-up surveys will be the primary population for the analysis. Three subgroups will be analyzed: the app group, the chatbot group, and the delay group.

Outcomes, Statistical Methods, and Statistical Analyses

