All outcomes will be presented using descriptive statistics. Binary and categorical variables will be presented using counts and percentages. SPSS 27 will be used for all statistical analyses.

Research Question 1: Do participants reduce their alcohol consumption more when using the app or the bot?

Hypothesis 1: Participants using either the app or bot will show a significantly greater reduction in alcohol consumption and alcohol related problems than participants in the delay group.

Method: Repeated Measures Anova

Baseline and Follow-up data from the Alcohol Use Disorder Identification Test (USAUDIT), Short Inventory of Problems-Revised (SIP-R), Readiness to Change Questionnaire (RTCQ), and Timeline Followback (TLFB) will be compared between app, chatbot, and delay groups. Consumption data used from the TLFB will include drinks per day, percentage of days abstinent, and heavy drinking days. Average drinks per day will be calculated from the reported last 14 days of drinks. Percentage of days abstinent will be calculated as the percentage of days in the recent 14 days that participants reported 0 drinks. Heavy drinking days will be calculated as the number of days in the past 14 days that participants report drinking more than 3 drinks if they are an assigned female at birth or 4 drinks if they are an assigned male at birth. Repeated measures ANOVA will be ran to identify if there is an interaction between time and group. An interaction would indicate a significant difference between app, bot, and delay groups in the difference of their baseline and follow-up drinking data.

Research Question 2: Do participants utilize the app and bot differently?

Hypothesis 2: Participants in the bot group will utilize the intervention significantly more than the app group due to the intervention's conversational interface.

Method: Independent sample t-test

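### Discretionary termination for exclusion criteria that develop after randomization, combined with a completers-only analysis, can lose participants for reasons that may be related to outcome

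*Combined protocol and SAP*

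**What the plan says.** Section 6, Participant Withdrawal or Termination: "An investigator may terminate participation in the study if the participant meets an exclusion criterion (either newly developed or not previously recognized"). The sentence goes on to require that the criterion be one "that precludes further study participation". The rule is permissive, sets no time limit relative to randomization, and does not list the criteria that count.

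Section 6, Participant Exclusion Criteria, includes:
- "in alcohol or drug abuse treatment currently"
- "having a moderate to severe level of alcohol use disorder, defined as having a score of 25 or higher on the USAUDIT"
- "more than 30 days abstinent at baseline"

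Only the third of these is tied to baseline.

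Section 9: "All randomized study participants who complete both the baseline and follow-up surveys will be the primary population for the analysis". The visible text has no analysis of all randomized participants and no method for missing data.

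USAUDIT is one of the Hypothesis 1 outcomes: "Baseline and Follow-up data from the Alcohol Use Disorder Identification Test (USAUDIT), Short Inventory of Problems-Revised (SIP-R"), together with readiness to change and the Timeline Followback, are compared across the three groups. Section 7, Follow-Up, places the repeat measurement at 4 months: "The US AUDIT, TLFB, SIP-R, and Readiness to Change questionnaires will be used for the follow-up assessments".

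The check-in call script in the appendix asks AUDIT items 1 to 3. If the total is 3 points above baseline, the caller offers to connect the participant with a treatment center, if wanted by a live handoff during the call.

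**The concern.** Exclusion criteria are normally applied once, at entry. This rule lets them be applied again after randomization, when they may reflect how the participant has fared. A participant whose drinking worsens and who then enters treatment newly meets an exclusion. If participation is terminated before the 4-month survey, the completers-only definition removes that participant from the primary analysis.

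The drinking-related criteria are also one-sided. Later abstinence cannot trigger the rule, because that exclusion refers to baseline. Treatment entry and a high USAUDIT can.

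Two things are at stake. Section 4, aim 3, lets the between-group result of this pilot decide the design of the next trial, so a distorted contrast would carry forward. Section 3 names worsening alcohol intake as a known risk, and participants lost in this way would be missing from the 4-month outcome comparison that could show it.

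**Working it through.** The plan gives no figure for termination, dropout, SD or effect size, so there is nothing of its own to reproduce. The check is a comparison of passages, followed by an illustration of scale on stated assumptions.

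**1. Can each criterion newly arise and be detected before month 4?**

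| Criterion (section 6) | Tied to baseline? | Detectable before the 4-month survey? | Analysed in section 9? |
|---|---|---|---|
| In alcohol or drug treatment | No | Yes; the check-in call may itself lead to it | No |
| USAUDIT 25 or higher | No | Not by any scheduled measurement in the visible text | Yes |
| More than 30 days abstinent | Yes | Cannot newly arise | Days abstinent is analysed |

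*Treatment.* A rise of 3 points on the call leads to an offer of treatment. A participant who accepts and enters treatment meets the exclusion, and an investigator may then terminate participation. No visible text says that the 4-month survey is still sent.

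*USAUDIT.* The full score is taken at prescreen and next in the 4-month survey. The call uses three items scored 0 to 6, so its maximum is 3 × 6 = 18 and it cannot itself show a 25. A participant first found at 25 or more in the 4-month survey, and who completes that survey, meets the section 9 population definition.

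**2. Scale, on assumptions only.** Take a normal outcome in SD units (higher is worse), 50 per arm as in section 6, two arms compared by a two-sided 5% t-test, and assume that those removed are the worst. The removal fractions q are assumed.

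*Removal in one arm only, no true effect.* The mean of that arm improves by φ(z)/(1 − q), where z is the 1 − q normal quantile. For q = 10%: 0.1755/0.90 = 0.195.

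*Same threshold in both arms, true d = 0.5.* With c the threshold that cuts off fraction q of controls, the control mean becomes −φ(c)/Φ(c) and the active mean becomes −0.5 − φ(c + 0.5)/Φ(c + 0.5). For q = 10%: −0.195 and −0.585, a difference of 0.39.

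| q (of 50) | One arm only: shift, SD | One arm only: type I error (simulated) | Both arms: apparent d when true d = 0.5 |
|---|---|---|---|
| 5% (2.5) | 0.11 | 0.09 | 0.43 |
| 10% (5) | 0.20 | 0.17 | 0.39 |
| 20% (10) | 0.35 | 0.43 | 0.33 |

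If only half of the tail is removed in one arm, type I error is about 0.07 (10% tail) or 0.12 (20% tail). With the common threshold, power at d = 0.5 falls from about 0.70 to 0.56 (10%) or 0.45 (20%).

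The two patterns act differently. Equal application attenuates a real effect, while unequal application can create a spurious one. Nothing in the documents says which would occur, or how often.

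**The case against.** The case against is substantial.

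- *The rule is narrower than it first looks.* Termination is optional, and the criterion must be one that rules out continuing. This stands. But the protocol never says which criteria do so, so the choice is left to judgement after randomization, and nothing visible says that the person deciding is unaware of the arm.
- *The documents lean towards keeping treated participants.* Section 7 plans the treatment-history form at follow-up as well as baseline, the call script answers worsening with a referral and no termination step, and section 7 describes follow-up for all participants. This shows that routine termination on treatment entry is not ordered. It does not rule termination out, and no sentence says that a terminated participant is still surveyed.
- *Deterioration is watched elsewhere.* The call asks about drinking and mood, and a DSMB meets twice a year. This stands, so it would be too strong to say that deterioration is hidden altogether.
- *The underlying weakness is the completers-only population.* Largely true. This rule is one route into that problem, but it has its own simple remedy.

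A reader might infer that everyone scoring 25 or more at month 4 is removed, and simulate a percentage shrinkage from that. The documents describe no such step, since those who complete that survey are in the primary population. A reader might also infer that several exclusions are outcomes. Of the two at issue, only USAUDIT is analysed in section 9. Treatment entry is an event after randomization and is not always a bad result. Nor can it be said that removal is more frequent in one arm: the visible script is worded for app users, and the text available for review does not show which arms are called or when.

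**Conclusion.** The concern holds in a limited form. Sections 6 and 9 together allow a participant to be lost from the primary analysis after randomization for a reason that may be related to outcome. The credible route is treatment entry, which the study's own check-in call may prompt. The USAUDIT route would need detection before month 4, which the visible schedule does not provide, or a discretionary exclusion after the survey, which the text does not describe.

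The size and direction of the bias cannot be derived from the documents. The tabulated figures rest on assumed removal fractions and on the removed participants being the worst. If those terminated resembled the rest of their arm, the loss would cost sample size and not cause bias. At 50 per arm, one participant is 2% of an arm; if that were the worst outcome, the shift would be about 0.05 SD. A few terminations applied unevenly could matter, and none at all would leave the analysis untouched. The change is worth making because it is specific and cheap, not because a large bias has been shown.

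**What to change.** 1. In section 6, state that termination for a criterion that develops after randomization does not end outcome collection. Unless consent is withdrawn, the participant is still sent the existing online 4-month survey and is analysed in the randomized arm. This concerns data collection only; whether the participant goes on using the app or chatbot is a separate clinical decision.
2. Report terminations by arm, reason and timing.
3. Reconcile the exclusion list, the termination rule, the section 9 population and the check-in script, so that it is clear which exclusions apply only at enrolment. Include the script's branch in which a distressed participant is told to stop using the app, which does not say whether follow-up continues.
4. Handle participants later found to have been ineligible at entry under a separate rule.

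The cost is a short protocol amendment, which section 10 requires the IRB to approve before use. The survey is already planned online, so no new instrument is needed.

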Phase II will entail a feasibility study that will contrast the Step Away chatbot with the Step Away app and a wait-list control condition, utilizing a randomized, controlled study design. A face-to-face control condition will not be utilized in this study as research has indicated that mobile health apps reach a different population of potential users whom we want to recruit for this study. A minimum of one hundred and fifty participants who are 18 years of age and older who screen positive for unhealthy alcohol use will be recruited throughout the U.S. with Facebook advertisements. All participants will complete an online, baseline research assessment and a follow-up at 4 months, allowing a minimum of 3 months of intervention use. Three months of intervention use will allow enough time for participants to utilize all aspects of the intervention system (the set-up phase), extended exposure to the daily assessment and weekly feedback functionality and provide a mid-length follow up period. Data from the app and chatbot usage will be continually uploaded to a secure server to determine usage and treatment fidelity information for each intervention. In addition, 10 participants in the chatbot and app conditions will be interviewed based on their degree of engagement with each intervention to obtain their perspectives on each intervention's usefulness and barriers to engagement. (At the 4-month

follow-up, all participants will be given the Substance Abuse and Mental Health Services Administration's (SAMHSA) national treatment locator helpline to identify treatment services in their area.)

Phase III will focus on quantitative and qualitative data analysis, manuscript development, conference presentations and preparation of a large-scale follow up grant.

All screening, baseline, and follow-up assessments will be performed online through Qualtrics.

Screening

All participants will be screened for eligibility. A copy of the screening questionnaire is available in the appendix.

Baseline

- The Timeline Followback (TLFB) will be used to gather information on alcohol and drug use. The TLFB will be used to calculate the following drinking variables: average (mean) drinks per week, days abstinent, and heavy drinking days. Heavy drinking days will be defined as days with 4 or more standard drinks for women and 5 or more standard drinks for men.
- Short Inventory of Problems – Revised (SIP-R) will be used to assess the adverse consequences of substance use.

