Utilization data will be collected from participants who use either the app or the chatbot. Three variables will be collected to measure utilization: total visits, duration of use, and total active days used. Total visits will be measured by the number of times a participant interacts with a feature of the app or the bot. Duration of use will be calculated as the amount of time in between a participants most recent visit to the app or bot and their date of installing the app or bot. Active days used will be calculated by the number of days a participant interacted with the app or bot. Utilization will be calculated for both app and bot users. Independent sample t-tests will be conducted between the means of each variable to determine if there were significant differences between app and bot users.

Research Question 3: Does utilization of the app or bot influence drinking outcomes?

Hypothesis 3: Utilization of the app or bot will mediate drinking outcomes, in that the higher the utilization of the intervention, the greater reduction of drinking the participant will have between baseline and follow-up

Method: Mediation analysis

Utilization data and TLFB data will be used in this analysis. A mediation analysis will be conducted with group as the independent variable, change in drinking as the dependent variable, and utilization as the mediator. Significant effects of usage on change in drinking will determine if utilization predicts change in drinking for either group. A significant indirect effect will determine if utilization mediates the relationship between group and outcome.

10. Ethics/Protection of Human Subjects

Ethical Standard

The investigator will ensure that this study is conducted in full conformity with Regulations for the Protection of Human Subjects of Research codified in 45 CFR Part 46, 21 CFR Part 50, 21 CFR Part 56, and/or the ICH E6.

Institutional Review Board

The protocol, informed consent form(s), recruitment materials, and all participant materials will be submitted to the IRB for review and approval. Approval of both the protocol and the consent form must be obtained before any participant is enrolled. Any amendment to the protocol will require review and approval by the IRB before the changes are implemented to the study. All changes to the consent form will be IRB approved; a determination will be made regarding whether previously consented participants need to be re-consented.

Informed Consent Process

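### RQ2 (app versus chatbot use) appears limited to survey completers although its outcomes are server-logged, and the plan does not say how assigned participants who never install are counted

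*Combined protocol and SAP*

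**What the plan says.** Section 9 (Statistical Considerations) opens with its only population definition: "All randomized study participants who complete both the baseline and follow-up surveys will be the primary population for the analysis". It stands ahead of all three research questions, and neither a second population nor an exception follows.

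Research Question 2 in the same section is worded in two ways:

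- The hypothesis is by group: "Participants in the bot group will utilize the intervention significantly more than the app group".
- The method is by use: "Utilization data will be collected from participants who use either the app or the chatbot", with t-tests to "determine if there were significant differences between app and bot users".

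The outcomes are these: "Three variables will be collected to measure utilization: total visits, duration of use, and total active days used". Duration is the time between the "most recent visit to the app or bot and their date of installing the app or bot".

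Section 7 (Study Procedures and Schedule) separates the two data streams. For use: "Data from the app and chatbot usage will be continually uploaded to a secure server to determine usage and treatment fidelity information". For questionnaires: "All screening, baseline, and follow-up assessments will be performed online through Qualtrics". The follow-up survey goes out 4 months after enrolment. Section 10 (Consent Procedures) places randomization after the baseline assessment.

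The check-in call script in the appendix has a branch for participants who have not yet downloaded the product.

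**The concern.** Because baseline comes before randomization, the completer rule removes randomized people only through non-return of the 4-month survey. RQ1 and RQ3 need follow-up drinking data, so they cannot avoid that loss. RQ2 can: its outcomes are already held for people who do not return the survey.

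Survey return happens after assignment and may well track engagement. Selecting on it can undo the balance that randomization gave the app and chatbot arms. Selecting on installation can do the same, and the plan does not say whether an assigned non-installer counts as zero, as missing or as excluded. Duration has no value at all for someone with no install date.

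Section 4 puts engagement, with fidelity and alcohol outcomes, at the centre of the trial, and aim 3 uses the pilot results to shape the next trial. A distorted use contrast would therefore feed into that planning.

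**Working it through.** The plan states no effect size, SD, return rate or uptake rate, so it has no figure of its own to reproduce. The only numerical input from the documents is 50 per arm (Section 6, Target Sample Size). Everything else below is assumed.

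**1. Which outcomes need the survey?** Drinking change (RQ1, RQ3) does, through Qualtrics. Visits, duration and active days (RQ2) do not, since they come from the server log. The completer rule is needed for the first set only.

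**2. Spurious difference from selecting on survey return.** Model: use has SD 1 and the same mean in both arms, and the log-odds of returning the survey rise by b per SD of use. The figures are the difference in mean use among completers.

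| b in the two arms | Return | Spurious difference (SD) | SE (SD) | Ratio |
|---|---|---|---|---|
| 1.0 vs 0.5 | 85 / 70 / 60% in both arms | 0.059 / 0.111 / 0.143 | 0.210 / 0.228 / 0.244 | 0.28 / 0.49 / 0.59 |
| 1.0 vs 0 | 85 / 70 / 60% in both arms | 0.132 / 0.254 / 0.332 | 0.212 / 0.231 / 0.248 | 0.62 / 1.10 / 1.34 |
| 1.0 in both | 85% vs 60% | 0.200 (lower-return arm looks higher) | 0.222 | 0.90 |
| 1.0 in both | 70% in both arms | 0.000 | | |

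Analysing everyone assigned gives a bias within 0.002 SD in every case.

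**3. Effect on the nominal 5% t-test, no true difference.**

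| Scenario | Normal use | Skewed (lognormal) use |
|---|---|---|
| 70% return, b 1.0 vs 0.5 | 8% | 5% |
| 70% return, b 1.0 vs 0 | 19% | 11% |
| 85% vs 60% return, b 1.0 in both | 14% | 10% |
| Everyone assigned | 5% | about 4% |

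Visits and active days are counts and are likely to be skewed, so the right-hand column is probably nearer the truth.

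**4. Selecting on installation.** Suppose uptake is 90% in one arm and 70% in the other, and use per person assigned is equal. Among users, the lower-uptake arm then looks 0.9/0.7 = 1.286 times as active, or 29% higher. Now score non-installers 0 but keep completers only, with installers returning 85% and non-installers 50%. Installers make up 0.765/0.815 = 0.939 of completers in one arm and 0.595/0.745 = 0.799 in the other. The lower-uptake arm looks (0.799/0.7)/(0.939/0.9) = 1.094 times as active, or 9% higher. With equal uptake there is no distortion.

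**5. Precision if everyone installs.** SE = sqrt(2/n) in SD units. For n = 50 / 42.5 / 35 / 30 (100 / 85 / 70 / 60% return) it is 0.200 / 0.217 / 0.239 / 0.258. Power for a 0.5 SD difference is 70 / 63 / 54 / 48%.

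**6. Precision once zeros are counted.** Assume a difference of 0.5 SD among installers and an SD equal to the lower arm's mean, so the installer means are 1 and 1.5 with SD 1. If p is the share of installers among those analysed, the difference is 0.5p and the arm variances are 2p − p² and 3.25p − (1.5p)². Return is as in step 4.

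- Uptake 80%, everyone assigned (p = 0.80, n = 50): 0.400 / sqrt((0.960 + 1.160)/50) = 0.400/0.206 = 1.94, power about 49%.
- Uptake 80%, completers (p = 0.68/0.78 = 0.872, n = 39): 0.436 / sqrt((0.984 + 1.123)/39) = 0.436/0.232 = 1.88, power about 46 to 47%.
- Uptake 70%, everyone assigned (p = 0.70, n = 50): 0.350/0.204 = 1.71, power about 40%.
- Uptake 70%, completers (p = 0.799, n = 37.25): 0.399/0.239 = 1.67, power about 38 to 39%.

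The gain is about 1 to 3 points. A users-only comparison at 80% uptake (n = 40 per arm) would have 60% power, but for a different question.

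**The case against.** **No RQ2 sentence imposes the completer rule.** It follows from one general sentence that speaks of the primary population, and RQ2 has a more specific source of its own, people who use a product. If that governs, completer status may not matter to RQ2. This stands as a limit on certainty: a reader might infer that RQ2 is expressly restricted to completers, and the text does not go that far. But no other population is defined, and the RQ2 wording brings in the installation question instead.

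**The word users may simply mean the two product arms.** That is possible. The non-installer problem then shrinks to a missing rule for duration, and the completer condition remains.

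**Safeguards exist.** Section 6 excludes people unwilling or unable to complete follow-up, and the check-in script has staff help with downloading. Both should reduce loss, but neither says who is analysed.

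**The sizes may be small.** This stands in good part. Bias is nil when return and dependence match across arms, the largest values need dependence in one arm only, and skewed use weakens the effect on the test. The power gain nearly disappears once zeros are counted.

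**It is a pilot.** True, and a reader might infer that the wrong product could be taken forward. Aim 3 does not say which outcome decides, so the documents do not support that.

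**Conclusion.** The point holds as a gap in how the RQ2 population is defined, and it should be fixed. The only stated population appears to apply to RQ2 without need, and RQ2's own wording describes a different one that is not reconciled with it.

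Under the assumed return rates of 60 to 85%, the spurious difference is about 0.06 to 0.33 SD if return depends on use differently by arm, and 0.20 SD at 85% versus 60% return with the same dependence. It is nil when both match. False-positive rates in the three scenarios tested are 8, 19 and 14% with normal use, and about 5, 11 and 10% with skewed use. The power gain from analysing everyone is at most 70% against 63, 54 or 48% when everyone installs, and about 1 to 3 points at 70 to 80% uptake. All of these rest on assumed rates, and the direction of any bias cannot be known from the documents.

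A reader might also infer that RQ1 should leave the completer population on the same argument. It does not carry over. RQ1 needs the follow-up drinking data, and whether a baseline-adjusted model or the planned change comparison is less biased depends on whether loss follows the follow-up level of drinking or the change in it.

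**What to change.** State an RQ2 population in Section 9:

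- Analyse everyone randomized to app or chatbot, as assigned, whether or not the follow-up survey is returned.
- Count server-logged use over one common window, from randomization to month 4.
- Score non-installers 0 visits, 0 active days and 0 duration, and report installation by arm beside these, so that a non-installer is not confused with someone who installed and visited once.
- Count use up to withdrawal or deletion of the product, and zero after that.
- State that wait-list participants, who receive the app after 3 months, are not part of the app arm.
- Report users-only and completers-only results as secondary.

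The cost is SAP wording and two secondary tables, with no new data. There are downsides. Means fall and skew rises because zeros are counted. Power can be lower than in a users-only comparison (about 49% against 60% at 80% uptake in the example above). The primary RQ2 question becomes use per person assigned, and use per user moves to secondary.
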